The early stopping rule for safety/toxicity will be assessed for each patient after cycle 1: the expected rate of unacceptable toxicity should not be $\geq 33\%$. Note: The phase II portion of the study will use the DLT definition to define unacceptable toxicity. If more than the specified number of patients has significant treatment related toxicities, patient accrual will be halted and a full review of the data by the Data Safety Monitoring Committee (DSMC) will be mandated. Patient accrual will not resume until approved by the DSMC to do so.

In addition, cumulative safety data will be reviewed on a quarterly basis in order to identify safety concerns that may emerge due to cumulative exposure.

Trial Statistical Analysis Plan

Patient demographic and baseline characteristics, including age, gender, medical history, and prior therapy, will be summarized using descriptive statistics. For continuous variables, descriptive statistics (number [n], mean, standard deviation, standard error, median (range) will be provided. For categorical variables, patient counts and percentages will be provided.

Phase I Analysis: Observed toxicities will be summarized in terms of type (organ affected or laboratory determination), severity, time of onset, duration, probable association with the study treatment and reversibility or outcome. Baseline information (e.g. the extent/type of prior therapy) and demographic information will be presented as well to describe the patients treated in this study.

Phase II Analysis: The complete remission rate (CR+CRi) will be calculated as the percent of evaluable patients; exact 95% confidence intervals will be calculated for these estimates. Response rates will also be evaluated based on number and type of prior therapy(ies). Time to response, duration of response, and survival will be estimated using the product-limit method of Kaplan and Meier.

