5.2 Treatment cycle definition

Participants will be treated in 28-day treatment cycles until disease relapse, progression, unacceptable toxicity, withdrawal of consent, or other protocol specified parameters to stop treatment.

Once a treatment cycle has began (i.e. the Day 1 dose administered) if there is a hold in administering the study agent (see section 6.3.2), **missed doses may be made up if the criteria to resume treatment are met within 48 hours, or by Day 5 of the treatment cycle, whichever is later**. Otherwise missed administrations will not be made up, and treatment will resume with the next cycle (assuming start of cycle criteria are met). Should a hold or delay in treatment occur, after the last dose is administered in a given cycle, there will be a 21 day break, which may result in a delay in the start of the subsequent cycle.

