5.7 Duration of Therapy & Criteria for Removal from Study Treatment

Duration of therapy will depend on individual response, evidence of disease progression and tolerance, or completion of 4 cycles of study treatment. Patients may continue for up to 4 cycles of treatment unless unacceptable toxicity or disease relapse/progression. In the absence of treatment delays due to adverse events, treatment may continue until one of the following criteria applies:

- Participant demonstrates disease progression.
- Intercurrent illness that prevents further administration of treatment
- Unacceptable adverse event(s) (see Section 13.2, 6.3.1)
- Participant withdraws from the treatment phase of the study
- General or specific changes in the participant's condition that render the participant unacceptable for further treatment in the opinion of the treating investigator.

Documentation of the reason for discontinuing therapy and the date effective should be made in the medical record and appropriate eCRF. The participant should then proceed to off-treatment procedures for safety monitoring and follow-up procedures. The participant status is to be modified in the MIDAS system once the off-treatment period is completed. Alternative care options will be discussed with the participant.

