- c. Participants will receive a maximum of 4 study cycles. Participants who experience unacceptable toxicity or disease progression after cycle 2 will forgo additional treatment cycles and proceed to the 30-day-follow-up visit. There will be a +7 day window for start of cycles 2-4.
- d. Day 1 assessments (including EKG) to be performed prior to Day 1 drug. Start of cycle criteria (Section 6.2) must be met before administering Day 1 study agent.

- e. Study agent will be administered daily for five consecutive days. EKG will be performed and reviewed prior to study drug administration. See section 5.2: 'Treatment Cycle Definition' for additional detail regarding treatment administration timing in the event of a hold.
- f. Window for Day 8, 15, and Day 22 assessments is the stated day +/- 2 days. Bone marrow biopsy may be performed between days 22 and 28 after cycle initiation.
- g. Window for the 30-day Post Last Dose visit is +/- 2 days. All participants will be followed until resolution or stabilization of any related serious adverse events occurring during treatment or starting within 30 days of last study drug administration.
- h. Active follow-up will occur for participants who have completed EOT procedures and yet to demonstrate disease progression. The active follow-up visit will take place every 28 days (+/- 5 days) from the day of the EOT Day 30 visit. Active follow-up will continue until an alternative acute leukemia therapy has commenced or until disease progression or up to 2 years following first study agent administration.
- i. Survival follow-up will occur approximately every 3 months (+/- 14 days) from Off-Therapy date for survival status and will occur for up to 2 years following the participant's first study agent administration. Information will be obtained via medical record review, use of the social security registry, or by telephone contact.
- j. Documented informed consent to occur prior to any study related procedures that are not otherwise SOC.
- k. Medical history to include review treatment history for AML, relevant medical history pertaining to study eligibility, and demographic information.
- l. Concurrent medications, supportive care, blood products, or radiation therapy taken or administered during the trial will be documented in the subject's medical record using institutional documentation guidelines. See Section 5.11 for prohibited therapies.

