- v. Response assessment to use Döhner, 2010 criteria²⁴ detailed in Section 12.2. Response will be assessed at the end of each cycle/just prior to the start of each cycle. While response will be assessed at the end of Cycle 1, the result of the end of Cycle 1 response assessment will not affect whether or not a participant continues onto Cycle 2.
- w. See Section 5.5 for 8-chloro-adenosine administration details. Study agent will be administered daily for five consecutive days, unless there is a hold due to toxicity. See Section 5.2 for administration and day count when there is a hold in agent administration.
- x. For participants who unable to provide the full 10 ml of research bone marrow sample at pre-study (footnotes 't' and 'u'), 26 to 28 ml of peripheral blood will be collected into EDTA purple top tubes. Tubes will be inverted several times and then immediately placed on ice for transportation to [name] in Needleman room 1042. Notify [name] (or his representative) by e-mail to [contact] in advance of sampling (ideally at least a day in advance).
- y. For Cycle 1 only, blood will be collected for PK/PD analysis from a separate anatomic site (e.g. opposite arm) from site drug infusion at various time points. See Section 9.1.2 for details. Notify the CICSL ([name] or her representative) by e-mail to [contact] in advance of sampling (ideally at least a day in advance).
- z. Urine will be collected in 8 hr (+/- 30 min) sequential intervals (e.g. 0-8 hrs, 8-16 hrs, and 16-24 hrs) during the first 24 hours after the first dose of cycle 1. Urine may be maintained at RT, and should be brought to CICSL (Shapiro room 1042). Samples may be delivered to CICSL in a single batch.
 - aa. Inclusion/exclusion criteria are detailed in Section 3.
 - bb. See Section 4.3 for slot reservation and registration process. Registration is to occur prior to start of treatment. Documentation providing Investigator's confirmation that all eligibility criteria are met must be available and provided for registration.
 - cc. Participants will be monitored for anti-cancer treatments during Active Follow-Up. If other anti-cancer treatments (including HCT) are initiated, participants will be removed from Active Follow-Up and proceed to Follow-Up for Survival.
 - dd. Anti-cancer treatments will be collected until the participant completes the study.
 - ee. Survival information and reason for death will be collected until the participant completes the study.

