12.2 Response

The primary endpoint is complete remission rate (CR + CRi) and is based on the Döhner, 2010 criteria²⁴; calculated as the percent of evaluable patients that have confirmed CR or CRi.

Response criteria will be as follows:

CR: Bone marrow with < 5% blasts by morphology. ANC > 10³/µL, platelets ≥ 10⁵/µL

CRi: Bone marrow with < 5% blasts by morphology, not meeting blood count criteria for CR.

PR: Decrease of at 50% in bone marrow blasts

PD: Bone marrow blasts more than 20% and increase in blasts by over 50%.

HR: improvement in hematologic parameters, but not meeting criteria for PR.

Secondary activity endpoints for this study are as follows:

- Duration of response, defined as the time interval from the date of first documented response (CR+CRi) to documented disease relapse or death whichever occurs first.
- Overall survival, defined as the time interval from date of first dose of study drug to date of death from any cause.
- Event-free survival, defined as the time interval from date of first dose of study drug to first documented disease progression or death from any cause, whichever occurs first.
- Overall response rate (CR/CRI/PR), calculated as the percent of evaluable patients that have confirmed CR or CRi or PR.

12.3 Clinical Pharmacology Endpoints:

- For plasma PK, levels of 8-chloro-adenosine, its deaminated metabolite, 8-chloro-inosine, and its base 8-chloro-adenine will be quantitated in plasma during 5 days of therapy.
- For cellular PK, concentrations of 8-chloro-adenosine and 8-chloro-ATP will be quantitated in circulating leukemia cells in the peripheral blood.
- For urine PK, levels of 8-chloro-adenosine, its deaminated metabolite, 8-chloro-inosine, and its base 8-chloro-adenine will be quantitated in urine during the first 24 hours of therapy.
- For PD, the impact of therapy on endogenous ATP pools, as well as the effect on short-lived mRNA transcripts and proteins will be analyzed in circulating acute leukemia blasts.

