Phase II (Evaluable for Toxicity): Patients will be considered evaluable for toxicity if they receive any study drug. Patients enrolled/treated as part of the phase II study will not be replaced based on toxicity.

Phase I and II (Evaluable for Response): For the phase II portion, as part of the primary analysis, patients will be considered evaluable for response if they are eligible, have baseline disease assessments, and receive 2 cycles of protocol treatment or achieve a CR/CRI after 1 cycle of protocol treatment. Patients will have their response classified according to the Dohner 2010 criteria²⁴.

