13.7 Trial Statistical Analysis Plan

Patient demographic and baseline characteristics, including age, gender, medical history, and prior therapy, will be summarized using descriptive statistics. For continuous variables, descriptive statistics (number [n], mean, standard deviation, standard error, median (range) will be provided. For categorical variables, patient counts and percentages will be provided.

Phase I Analysis: Observed toxicities will be summarized in terms of type (organ affected or laboratory determination), severity, time of onset, duration, probable association with the study treatment and reversibility or outcome. Baseline information (e.g. the extent/type of prior therapy) and demographic information will be presented as well to describe the patients treated in this study.

Phase II Analysis: The complete remission (CR+CRi) rate will be calculated as the percent of evaluable patients; exact 95% confidence intervals will be calculated for these estimates. Response rates will also be evaluated based on number and type of prior therapy(ies). Time to response, duration of response, and survival will be estimated using the product-limit method of Kaplan and Meier.

Clinical Pharmacology Analysis Plan:

- Plasma, urine and cellular PK of 8-chloro-adenosine and metabolites will be quantitated as continual measurement variables as per assays described in Section 9.1.7.
- Descriptive statistics and graphical displays will be used to summarize levels of serum/urine 8-chloro-adenosine and its metabolites at each time point and to evaluate changes pre- post-treatment measurement. A paired t-test will be used to determine if there is a statistically significant change.
- Similar methods will be used to assess the PD impact of 8-chloro-adenosine on the cellular ATP pool and select short-lived mRNAs including corresponding proteins in AML blasts. Protein and mRNA levels will be summarized descriptively using means, medians, standard deviations and ranges.
- Summary statistics of the PK/PD parameters for the population will be derived from the parameters obtained from the individual patients.
- Results will also be summarized in terms of response and toxicity.

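### The primary CR/CRi rate drops treated non-responders who leave before two cycles but keeps one-cycle responders, so it is biased upward

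*Combined protocol and SAP*

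**What the plan says.** Section 12.2 describes the primary endpoint as a rate "calculated as the percent of evaluable patients that have confirmed CR or CRi". Section 13.7 repeats this for the analysis: the CR+CRi "rate will be calculated as the percent of evaluable patients; exact 95% confidence intervals will be calculated for these estimates". The synopsis analysis plan agrees.

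Section 13.1 (Evaluable for Response) and the matching synopsis text define the set for the primary analysis. The patient must be eligible, have a baseline disease assessment, and either "receive 2 cycles of protocol treatment or achieve a CR/CRI after 1 cycle of protocol treatment". The secondary overall response rate in section 12.2 also uses evaluable patients. Only the toxicity set takes in everyone who received any drug. OS and EFS run from the first dose.

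The design text counts differently. The stage 1 rule in section 13.1 looks at the first nine treated patients, and the Experimental Design Schema describes the 25 as participants treated at the RP2D.

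On who reaches cycle 2, footnote v of the Study Calendar says "the result of the end of Cycle 1 response assessment will not affect whether or not a participant continues onto Cycle 2". Footnote c says "Participants who experience unacceptable toxicity or disease progression after cycle 2 will forgo additional treatment cycles". Section 5.2 says "Participants will be treated in 28-day treatment cycles until disease relapse, progression, unacceptable toxicity, withdrawal of consent", and section 5.7 says "Patients may continue for up to 4 cycles of treatment unless unacceptable toxicity or disease relapse/progression"; neither limits this to the period after cycle 2.

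**The concern.** Among patients who receive only one cycle, membership of the denominator depends on the outcome being measured. A one-cycle patient in CR/CRi is counted. A one-cycle patient who dies, withdraws, or stops for toxicity or progression without CR/CRi is not. Deaths and stops for toxicity or progression are treatment failures, yet they vanish from the response rate.

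The phase II primary objective is to estimate this rate, in a single-arm trial that treats 30% as promising. Early failures still count in OS and EFS, but no planned analysis shows the response rate or its exact confidence interval with them included. A reader of the final report could not tell how much of the rate comes from the exclusion.

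**Working it through.** **The plan's own figures.**

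- Stage 1, nine patients, true rate 30%: P(at least one response) = 1 − 0.7^9 = 0.960. The stated 96% is correct for nine treated patients.
- Standard error with 25 in the denominator: the maximum is √(0.5 × 0.5 / 25) = 0.100. The stated limit of 10% is correct if all 25 count.

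**Direction of the bias.** Let r be the number of responders among 25 treated, and d the share of the 25 − r non-responders who never receive cycle 2. The cycle condition removes (25 − r)d patients, none of them responders:

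reported rate = r / [r + (25 − r)(1 − d)]

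This is at least r/25, and exceeds it whenever r > 0 and d > 0. No assumption about the size of d is needed for the direction.

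**Size.** The documents give no value for d. A range of 10% to 40% is assumed.

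| Share of non-responders lost (d) | True 20% (r = 5) | True 30% (expected r = 7.5) |
|---|---|---|
| 10% | 5/23 = 21.7% | 7.5/23.25 = 32.3% |
| 20% | 5/21 = 23.8% | 7.5/21.5 = 34.9% |
| 30% | 5/19 = 26.3% | 7.5/19.75 = 38.0% |
| 40% | 5/17 = 29.4% | 7.5/18 = 41.7% |

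For a true 20% to read as 25%, the denominator must be 5/0.25 = 20, so d = 5/20 = 25%. For it to read as 30%, the denominator must be 5/0.30 = 16.67, so d = 8.33/20 = 42%.

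**Exact (Clopper-Pearson) 95% intervals with five responders.**

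| Denominator | Interval |
|---|---|
| 25 | 6.8% to 40.7% |
| 23 | 7.5% to 43.7% |
| 19 | 9.1% to 51.2% |
| 17 | 10.3% to 56.0% |

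**Precision if 25 are treated and fewer are evaluable.** The maximum standard error √(0.25/n) is 10.4% at n = 23, 11.2% at n = 20 and 12.1% at n = 17. At a rate of 30% it is √(0.21/n), which is 10.0% at n = 21 and 10.2% at n = 20. At that rate the limit is passed only below 21 evaluable patients.

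**Which patients the 25 are.** Section 13.1 rules out replacement on grounds of toxicity and says nothing about patients not evaluable for response. One sentence in the synopsis (Phase II Design) counts phase I patients towards the 25 only if they had two or more cycles. The synopsis statistical section and sections 13.1 and 13.5 count all six without that condition. The documents therefore do not settle whether the 25 are treated or evaluable patients.

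**How many progressors are removed.** Footnotes v and c suggest that a patient progressing in cycle 1 may still receive cycle 2 and so stay in the denominator. Sections 5.2 and 5.7 end treatment at progression without that limit. The number lost through progression cannot be worked out until these passages agree. Losses through death, withdrawal or toxicity do not depend on that conflict.

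**The case against.** The strongest reply is that little turns on this rate. The only formal efficacy decision, the 0-of-9 rule, is worded on treated patients, and removing non-responders cannot create a response. No final test or threshold is attached to the CR/CRi rate; 30% is a planning reference, and the analysis is an estimate with an interval. The evaluable set is defined in advance, and an all-treated rate could be derived from the data collected. All of this is true. But estimating the rate is the primary objective, and an analysis that could be run is not one that is planned.

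The size is also open to challenge. Eligibility requires a life expectancy above three months, which is longer than two 28-day cycles, and excludes patients expected to have a transplant within 120 days. Footnote v keeps cycle 1 non-responders on treatment. At 10% to 20% loss, a true 20% moves by 2 to 4 points, against a sampling standard error of √(0.2 × 0.8 / 25) = 8 points. This stands: the larger shifts need about 40% of non-responders to miss cycle 2, and the documents neither support nor exclude that. Bias is not reduced by being smaller than sampling error, however, and the interval does not allow for it.

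Three narrower points also stand:

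- If the 25 are meant to be evaluable, the standard error holds and only the bias remains.
- The eligibility and baseline-assessment conditions could remove a responder, so the claim of one-way bias applies to the cycle condition alone.
- Counting every patient dosed at the RP2D would bring in phase I patients replaced for receiving under 80% of cycle 1. If they had little exposure, they could lower the chance of passing stage 1 with an active drug.

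**Conclusion.** The concern holds. The upward direction follows from the definition itself. The size rests on an assumed early loss: at 10% to 40% of non-responders, a true 20% reads as 22% to 29% and a true 30% as 32% to 42%. A true 20% would reach the promising 30% only at about 42% loss. The 96% and 10% design figures are correct on their own terms, and the stage 1 decision as worded is not biased by the evaluable definition. Any loss of precision depends on reading the 25 as treated patients. Because the primary estimate and its interval are affected and no other response analysis is planned, the definition needs to be changed.

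**What to change.** - In sections 12.2, 13.1 and 13.7 and the synopsis, define the primary denominator as all eligible patients who receive any dose at the RP2D, in phase I or II. Count anyone without a documented CR/CRi as a non-responder.
- Use this one set for the 0-of-9 rule and for the total of 25.
- Report the rate in the current two-cycle evaluable set as a sensitivity analysis.
- Remove the two-cycle condition on phase I patients from the synopsis, and state new enrolment as 9 and 25 minus the number already treated at the RP2D in phase I.
- Reconcile Study Calendar footnotes c and v with sections 5.2 and 5.7 on whether progression after cycle 1 ends treatment. No position is taken here on which rule should apply, and the new denominator works under either.

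The cost is wording only, and the total of 25 is unchanged. The reported rate will be somewhat lower, activity in patients who receive two cycles will appear only as a sensitivity analysis, and a few phase I patients with limited exposure may enter the denominator.

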The recommended phase II dose (RP2D) will generally be the MTD, but it may be less than the MTD based on a review of available data/cumulative toxicities and activity.

Phase II Design:

The phase II portion of this study will implement a Gehan two-stage design to estimate the response rate and to evaluate the activity of 8-chloro-adenosine when given as a single agent (Gehan, 1961). The phase II portion of the study is expected to enroll a minimum of 9 and a maximum of 25 patients. Patients treated at the RP2D in the phase I portion of the study, who receive at least 2 cycles of treatment, will count toward the 25 patients required. The sample size is based on the desire to estimate the response rate with at most 10% standard error, and early stopping if the treatment is unexpectedly ineffective.

At stage 1, 9 patients will be entered on the study. If 0 responses are seen in the first 9 patients treated, the study will be terminated and the true regimen response will be declared $\leq 30\%$. If at least 1 patient responds, the trial will continue to the second stage. Because patients treated during the phase I portion of the trial at the dose selected for the phase II trial will be counted ($n=6$), only 3 additional patients will be enrolled at stage 1. Under this design if the study agent is $>30\%$ effective, there would be 96% chance of at least one success.

At stage 2, 16 additional patients will be entered. This accrual provides for estimation of the response rate with no more than 10% standard error.

Endpoints:

Phase I:

The primary endpoint is toxicity. Toxicity will be graded according to the NCI-Common Terminology Criteria for Adverse Events version 4.03. Dose limiting toxicity (DLT) and moderate toxicity are defined in section 13.2 of the protocol. Note: The phase II portion of the study will use the DLT definition to define unacceptable toxicity. The MTD will be based on the assessment of DLT during cycle 1. All patients who are not evaluable for dose limiting toxicity will be replaced.

Phase II:

The primary endpoint is complete remission rate (CR/CRi) and is based on the Döhner et al. 2010 criteria²⁴. Response will be assessed at the end of each cycle/just prior to the start of each cycle. Secondary endpoints include: remission duration, survival (overall and event-free) and toxicity.

Clinical Pharmacology Endpoints:

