Phase II: The primary objective is to estimate the response rate and to evaluate the antitumor activity of 8-chloro-adenosine, in patients with relapsed or refractory acute myeloid or lymphoblastic leukemia. The primary endpoint is complete remission rate (CR/CRI) and is based on the Döhner, 2010 criteria²⁴. A cycle of treatment is 28 days. Each patient's disease status will be evaluated at baseline. Response will be assessed at the end of each cycle/just prior to the start of each cycle.

The phase II portion of this study will implement a Gehan two-stage design to estimate the response rate and to evaluate the activity of 8-chloro-adenosine when given as a single agent. The phase II portion of the study is expected to enroll a minimum of 9 and a maximum of 25 patients. The six patients treated at the RP2D in the phase I portion of the study will count toward the 25 patients required; given this, we expect to enroll only 19 new patients on the phase II trial. The sample size is based on the desire to estimate the response rate with at most 10% standard error, and early stopping if the treatment is unexpectedly ineffective.

At stage 1, 9 patients will be entered on the study. If 0 responses are seen in the first 9 patients treated, the study will be terminated and the true regimen response will be declared $\leq 30\%$. If at least 1 patient responds, the trial will continue to the second stage. Because patients treated during the phase I portion of the trial at the dose selected for the phase II trial will be counted ($n=6$), only 3 additional patients will be enrolled at stage 1. Under this design if the study agent is $>30\%$ effective, there would be 96% chance of at least one success.

At stage 2, 16 additional patients will be entered. This accrual provides for estimation of the response rate with no more than 10% standard error.

Phase II (Evaluable for Toxicity): Patients will be considered evaluable for toxicity if they receive any study drug. Patients enrolled/treated as part of the phase II study will not be replaced based on toxicity.

Phase I and II (Evaluable for Response): For the phase II portion, as part of the primary analysis, patients will be considered evaluable for response if they are eligible, have baseline disease assessments, and receive 2 cycles of protocol treatment or achieve a CR/CRI after 1 cycle of protocol treatment. Patients will have their response classified according to the Dohner 2010 criteria²⁴.

Sample Size

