Phase I (Evaluable for Toxicity): Patients will be considered evaluable for toxicity if they receive any study drug. To be evaluable in the context of dose escalation, a patient must receive at least 80% of 8-chloro-adenosine and be followed for the full 28 days during cycle 1 or experience a DLT during the first cycle of therapy. All patients who are not evaluable for DLT will be replaced.

Phase II:

The primary objective is to estimate the response rate and to evaluate the antitumor activity of 8-chloro-adenosine, in patients with relapsed or refractory acute myeloid or lymphoblastic leukemia. The primary endpoint is complete remission rate (CR/CRI) and is based on the Döhner, 2010 criteria²⁴. A single cycle of treatment will be given in a 28 day cycle. Each patient's disease status will be evaluated at baseline. Response will be assessed at the end of each cycle/just prior to the start of each cycle.

The phase II portion of this study will implement a Gehan two-stage design to estimate the response rate and to evaluate the activity of 8-chloro-adenosine when given as a single agent [23]. The phase II portion of the study is expected to enroll a minimum of 9 and a maximum of 25 patients. The six patients treated at the RP2D in the phase I portion of the study will count toward the 25 patients required; given this, we expect to enroll only 19 new patients on the phase II trial. The sample size is based on the desire to estimate the response rate with at most 10% standard error, and early stopping if the treatment is unexpectedly ineffective.

At stage 1, 9 patients will be entered on the study. If 0 responses are seen in the first 9 patients treated, the study will be terminated and the true regimen response will be declared $\leq 30\%$. If at least 1 patient responds, the trial will continue to the second stage. Because patients treated during the phase I portion of the trial at the dose selected for the phase II trial will be counted ($n=6$), only 3 additional patients will be enrolled at stage 1. Under this design if the study agent is $>30\%$ effective, there would be 96% chance of at least one success.

At stage 2, 16 additional patients will be entered. This accrual provides for estimation of the response rate with no more than 10% standard error.

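### The primary CR/CRi denominator drops treated patients who stop before receiving 2 cycles without a remission but keeps one-cycle responders, so the reported rate can exceed the rate among those treated.

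*Combined protocol and SAP*

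**What the plan says.** Section 12.2 defines the primary endpoint, the CR + CRi rate, as "calculated as the percent of evaluable patients that have confirmed CR or CRi". Section 13.7 repeats the denominator for the phase II analysis: the "rate will be calculated as the percent of evaluable patients; exact 95% confidence intervals will be calculated for these estimates".

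Section 13.1 (Evaluable for Response), with the same text in the Synopsis under Statistical Considerations, sets the evaluable set for the primary analysis. A patient must be eligible, have a baseline disease assessment, and "receive 2 cycles of protocol treatment or achieve a CR/CRI after 1 cycle of protocol treatment". No response analysis of all treated patients is described, and nothing says that early stoppers count as non-responders.

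The stage 1 rule in section 13.1 is worded differently: "If 0 responses are seen in the first 9 patients treated", the study ends.

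On carrying phase I patients into phase II, the Synopsis contains two statements. Under Phase II Design, patients treated at the RP2D "who receive at least 2 cycles of treatment, will count toward the 25 patients required". Under Statistical Considerations, and again in sections 13.1 and 13.5, the condition is absent: "The six patients treated at the RP2D in the phase I portion of the study will count toward the 25 patients required".

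**The concern.** Whether a patient with fewer than 2 cycles is counted depends on that patient's outcome: in CR/CRi after cycle 1, counted; not in CR/CRi, removed. Those removed for short treatment are by construction failures on the primary endpoint.

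The protocol itself foresees early stops. Section 5.7 ends treatment for progression, intercurrent illness, unacceptable adverse events, withdrawal or a change in condition. Sections 6.2 and 6.3.1 require permanent discontinuation if a hold has not resolved by Day 49. The population has relapsed or refractory AML, with a required life expectancy of only more than 3 months. A patient stopped by drug toxicity before cycle 2 counts in the safety set, where any dose is enough, but not in the efficacy denominator.

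The phase II primary objective is to estimate the response rate, so an upward shift affects the trial's main output. If excluded patients are not replaced, the sample size behind the precision target also shrinks.

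**Working it through.** **Inputs from the plan (section 13.1).** Stage 1 has 9 patients; stage 2 adds 16, for 25 in all; the response rate of interest is 30%; the target standard error is at most 10%. The number of treated non-responders who stop before receiving 2 cycles, *x*, is not given and is assumed below.

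**The plan's own figures.**
- Chance of at least one response in 9 at 30%: 1 − 0.7^9 = 0.9596, matching the stated 96%.
- Largest standard error at n = 25: √(0.5 × 0.5 / 25) = 0.100, matching the stated 10%.

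**Direction.** With r responders among N treated, the rate among those treated is r/N and the rate under the rule is r/(N − x). For r ≥ 1 and x ≥ 1 the second is larger. With N = 25 the multiplier is 25/(25 − x): 25/24 = 1.04, 25/21 = 1.19, 25/17 = 1.47.

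**Size, for an assumed 5 responders among 25 treated (exact 95% intervals).**

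| Excluded (x) | Rate | 95% CI |
|---|---|---|
| 0 | 5/25 = 20% | 7–41% |
| 4 | 5/21 = 24% | 8–47% |
| 8 | 5/17 = 29% | 10–56% |

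**Standard error if excluded patients are not replaced, √(p(1 − p)/n).**

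| n | p = 0.5 | p = 0.30 |
|---|---|---|
| 25 | 10.0% | 9.2% |
| 24 | 10.2% | – |
| 21 | 10.9% | 10.0% |
| 20 | – | 10.2% |
| 17 | 12.1% | 11.1% |

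At p = 0.5 the target allows no exclusions; at p = 0.30 it allows 4. Section 13.1 rules out replacement on toxicity grounds and does not address patients who are not evaluable for response. Replacing them would restore n but leave the selection in place.

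**When the exclusion window closes.** The rule uses the verb *receive*. Drug is given on days 1–5 of a 28-day cycle. If receiving 2 cycles means being given the cycle 2 doses, then without delays the window closes at about day 28 + 5 = 33. If it means completing both cycles, it closes at day 2 × 28 = 56. The text does not say which.

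**Phase I carry-over.** The Phase II Design condition in the Synopsis requires at least 2 cycles and has no CR/CRi exception. It can therefore remove one-cycle responders as well as non-responders. Table 6.3.2, for example, stops further cycles for a patient with under 5% marrow blasts whose related grade 3 or higher cytopenia has not resolved by day 49, and under section 12.2 such a patient may be a CRi. The two Synopsis statements conflict, but the direction of any effect on the rate is not fixed.

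**The case against.** The strongest reply is that the study calendar limits early loss. Footnote v says "the result of the end of Cycle 1 response assessment will not affect whether or not a participant continues onto Cycle 2", and footnote c is consistent with it: "Participants who experience unacceptable toxicity or disease progression after cycle 2 will forgo additional treatment cycles". Read as the specific rule, these send a cycle 1 progressor on to cycle 2 and so into the denominator. That stands as partial mitigation. It does not cover death, toxicity, intercurrent illness or withdrawal. Sections 5.2 and 5.7 end treatment at progression with no cycle 1 exception, and nothing says which text governs. The eligibility criteria on life expectancy and on transplant planned within 120 days also limit early stopping, to an unknown extent.

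A second reply is that an evaluable-patient rate is common in phase II. It is reasonable to report one. The difficulty is that it is the only response rate specified, with a criterion that treats responders and non-responders unequally.

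A third is that the consequences are limited. That is largely right: the illustrative intervals overlap widely, and overall and event-free survival run from first dose, so early failures are not defined out of them (though their analysis population is not stated).

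Three stronger readings are tempting and are not supported:
- A reader might infer that the rule distorts the stage 1 decision or a final claim of activity. Stage 1 is worded on patients treated, and no success threshold is stated at 25.
- A reader might infer that everyone who does not complete 56 days without remission is excluded. The text says *receive*, which may be satisfied once the cycle 2 doses are given.
- A reader might take the Synopsis carry-over condition as a second source of upward bias. It can remove responders too.

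**Conclusion.** The concern holds for the primary estimate. As written, the plan removes only patients without CR/CRi for having received fewer than 2 cycles, so the reported rate exceeds the rate among eligible, baseline-assessed treated patients whenever there is at least one responder and one such exclusion. The direction is certain under that condition; the size is not, because the documents give no early-stop counts. On the assumed 4 to 8 exclusions among 25 treated, a 20% rate would be reported as 24% to 29%. Without replacement, the 10% standard error fails from the first exclusion in the worst case and from the fifth at a 30% response rate. The carry-over conflict is a separate inconsistency that needs resolving, without a known direction of bias. The rule should be changed, but it does not undermine the design.

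**What to change.** In section 13.1 and the matching Synopsis text, state that every eligible patient treated at the RP2D with a baseline disease assessment who stops before receiving 2 cycles without CR/CRi, for any reason, stays in the primary denominator as a non-responder. Report the present two-cycle evaluable rate as a sensitivity analysis, and say there whether receiving a cycle means being given its doses or completing its 28 days.

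In the Synopsis, Phase II Design, delete the two-cycle condition on phase I patients so that it agrees with Statistical Considerations and section 13.1. Those sections speak of six patients, but patients not evaluable for DLT are replaced, so more than six may be treated at the RP2D. State that the replaced patients are counted as well.

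Aligning sections 5.2 and 5.7 with calendar footnotes c and v is a separate tidy-up.

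The cost is protocol wording, with no added visits or data. The estimate may be lower, and some patients who stop for reasons unrelated to the drug will count as failures; the sensitivity analysis shows how much that matters.
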